11.2. Response Criteria

The irRC criteria for assessing systemic disease response (including only non-irradiated lesions) can be seen in the following table:

New, measurable lesions (ie, $\geq 5 \times 5$ mm)	Incorporated into tumor burden
New, non-measurable lesions (ie, $< 5 \times 5$ mm)	Do not define progression (but preclude irCR)
Non-index lesions	Contribute to defining irCR (complete disappearance required)
irCR	Disappearance of all lesions in two consecutive observations at least 4 weeks apart
irPR	$\geq 50\%$ decrease in tumor burden compared with baseline in two observations at least 4 weeks apart
irSD	Neither sufficient decrease in tumor burden to qualify as irPR

	nor sufficient increase in tumor burden to qualify as irPD.
irPD	$\geq 25\%$ increase in tumor burden compared with nadir (at any single time point) in two consecutive observations at least 4 weeks apart.

Examples of irRC overall response³⁷:

Measurable response Index and new, measurable lesions (tumor burden),* %	Nonmeasurable response		Overall response Using irRC
	Non-index lesions	New, nonmeasurable lesions	
↓100	Absent	Absent	irCR [†]
↓100	Stable	Any	irPR [†]
↓100	Unequivocal progression	Any	irPR [†]
↓≥50	Absent/Stable	Any	irPR [†]
↓≥50	Unequivocal progression	Any	irPR [†]
↓<50 to <25↓	Absent/Stable	Any	irSD
↓<50 to <25↓	Unequivocal progression	Any	irSD
≥25↓	Any	Any	irPD [†]

*Decreases assessed relative to baseline, including measurable lesions only (>5 x 5 mm).
†Assuming response (irCR) and progression (irPD) are confirmed by a second, consecutive assessment at least 4 wk apart.

RECIST version 1.1 will be used to assess the local response of irradiated lesions only, taking as reference the baseline largest diameter:

Complete Response (CR)	Disappearance of the irradiated lesion
Partial Response (PR)	$\geq 30\%$ decrease in the single largest diameter of the irradiated lesion
Stable Disease (SD)	Neither sufficient decrease in diameter to qualify as PR nor sufficient increase in diameter to qualify as PD
Progressive Disease (PD)	$\geq 20\%$ increase in the single largest diameter of the irradiated lesion. In addition to the relative increase of 20%, the sum must also demonstrate an absolute increase of at least 5 mm (0.5 cm).

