5.3. Subsequent Response-Adapted Radiation Therapy

Any patient who completes the initial course of radiation therapy and continues on one of the immune checkpoint inhibitors described above will be eligible for subsequent course(s) of radiation therapy to a different lesion that was not previously irradiated based on the results of follow-up imaging studies detailed below and in section 11.

- Patients with a partial or complete response per irRC criteria will be observed without any further radiation therapy until progression.
- Patients with stable disease per irRC criteria will undergo an additional course of radiation therapy given concurrently with the next cycle of immune checkpoint

- therapy, and then continue the immune therapy as above. Each subsequent course of radiation therapy should ideally be at least 2 months after completion of the prior course of radiation therapy, but is left at the discretion of the treating physician depending on the patient's palliative needs. Day 1 of radiation should be on Day 1 of the next cycle of immune therapy.
- Patients with progressive disease at any time per irRC criteria will undergo a final course of radiation therapy. This may be given concurrently with a final cycle of immune therapy or as stand-alone treatment within 6 weeks after discontinuation of immune therapy but before an alternative systemic therapy is initiated.

Please see Section 5.5 below regarding situations in which these subsequent courses of radiation therapy may be withheld. Each subsequent course of radiation therapy should be given in a similar style as detailed for the initial course of radiation therapy above. In patients with a mixed response to therapy, preference will be given to an enlarging tumor (rather than one that is stable or decreasing in size) as the site of treatment. Reimaging will again be obtained after completion of the radiation therapy with timing at the discretion of the treating physicians, and the same response-adapted approach to decision making for further courses of radiation therapy will be carried out as described above.

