11. MEASUREMENT OF EFFECT

11.1. Antitumor Effect

11.1.1. Imaging Modalities

At baseline and follow-up, systemic response (for unirradiated lesions) and local response (for irradiated lesions) will be assessed using FDG-PET/CT (preferred) or CT scan of the chest/abdomen/pelvis. Ideally IV contrast and CT slice thickness $\leq 5\text{mm}$ will be used for either type of study. Images will be acquired according to the standard of care schedule used for patients receiving immune checkpoint therapy, at intervals of 4 months or less after initiation of immune therapy. In the event of an imaging study showing disease progression, a confirmatory scan is recommended at least 4 weeks later to confirm progression. The same method of assessment and technique should be used to characterize each index lesion at baseline and during follow-up. All measurements should be recorded in metric notation and specified to the nearest millimeter. All baseline evaluations should be performed as closely as possible to the beginning of treatment and never more than 4 weeks before the beginning of the treatment. Imaging-based evaluation is preferred to evaluation by clinical examination unless the lesion(s) being followed cannot be imaged but are assessable by clinical exam.

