Measureable lesions on follow-up imaging: Per irRC specifications, new measureable lesions on follow-up imaging will be defined as being $\geq 5 \times 5$ mm in size

Index lesions: All measurable lesions up to a maximum of 10 visceral lesions (≤ 5 per organ) and 5 cutaneous lesions, should be identified as index lesions and recorded and measured at baseline. Target lesions should be selected on the basis of their size (lesions with the longest diameter), be representative of all involved organs, and lend themselves to reproducible repeated measurements. It may be the case that, on occasion, the largest lesion does not lend itself to reproducible measurement in which circumstance the next largest lesion which can be measured reproducibly should be selected. It is preferable to exclude cystic metastases as index lesions if other non-cystic lesions are available. Prior to selecting index lesions a decision should be made on which lesion will receive an initial course of radiation therapy, as this lesion is not eligible to be considered as an index lesion to assess response to immune therapy. If any subsequent course(s) of radiation therapy are given to what was previously considered an index lesion, this lesion will no longer be considered an index lesion for subsequent systemic response assessment. The rationale for this is that including irradiated lesions in response assessment would bias the assessment of a systemic effect.

Tumor Burden: At the baseline tumor assessment, the sum of the products of the two largest perpendicular diameters (SPD) of all index lesions is calculated. At each subsequent tumor assessment, the SPD of the index lesions and of new, measurable lesions are added together to provide the total tumor burden: $\text{Tumor Burden} = \text{SPD}_{\text{index lesions}} + \text{SPD}_{\text{new, measurable lesions}}$.

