13.3. Methods for Analysis

Data will be summarized with respect to baseline characteristics and safety measurements using descriptive statistics (quantitative data) and contingency tables (qualitative data). The safety analysis will consist of AE summaries (frequency tables based on CTCAE grades) and laboratory abnormalities summary. For the primary endpoint, the response rate and its 95% confidence interval will be estimated with a binomial distribution. Univariate and multivariate logistic regression model will be used to assess the association between response and several radiotherapy variables (biologic effective dose,

number of lesions treated, sequence of radiation and immune therapy), tumor variables (irradiated tumor site, size, growth rate, histology, PD-L1 status, local response, extent of prior chemotherapy use, and biologic correlates), and patient variables (age, smoking status, and other factors associated with secondary immunodeficiency). A predictive nomogram for response will be developed based on the outcome of the multivariate analysis. In the data analysis on the secondary endpoints, the Kaplan-Meier method will be used to estimate overall survival and progression-free survival. Wilcoxon signed-rank test for paired data will be used to assess the change of quality of life scores between two visits. Since the lung cancer score (LCS) of the FACT-L focuses on lung cancer symptoms, this will be used for the primary QOL endpoint; however, the more general subscales of physical and functional well-being on the Trial Outcome Index (FACT-TOI) will also be collected. A difference of 3 LCS points will be considered clinically significant.¹²⁻¹³ Where applicable, comparison will be made to previous randomized trials assessing immune checkpoint inhibitors alone in a comparable patient population.

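### Local response of lesions irradiated in later courses is graded against the pre-treatment baseline diameter, so a lesion whose size changed before its own course can be misgraded.

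*Combined protocol and SAP*

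**What the plan says.** Section 11.2 states: "RECIST version 1.1 will be used to assess the local response of irradiated lesions only, taking as reference the baseline largest diameter". The cut-offs that follow are a decrease of at least 30% for PR, and for PD an increase of at least 20% that is also at least 5 mm. CR is disappearance of the lesion.

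Baseline imaging is tied to the start of treatment. Section 11.1.1 requires it "never more than 4 weeks before the beginning of the treatment". Section 11.1.2 uses the word for a single assessment: "At the baseline tumor assessment, the sum of the products of the two largest perpendicular diameters (SPD) of all index lesions is calculated".

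Section 5.3 offers "subsequent course(s) of radiation therapy to a different lesion that was not previously irradiated". For patients in stable disease, a further course "should ideally be at least 2 months after completion of the prior course of radiation therapy". In a mixed response, "preference will be given to an enlarging tumor (rather than one that is stable or decreasing in size) as the site of treatment". A final course is given at progression. Section 11.1.2 removes an index lesion that is later irradiated from the systemic assessment, but sets no new reference for its local response. Section 5.1.2 foresees treating bone or brain metastases that develop on study.

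Local response is listed as a predictor of systemic response in 1.2. The logistic models of 13.3 include it among the tumor variables ("PD-L1 status, local response, extent of prior chemotherapy use, and biologic correlates"), and a nomogram is to be built from the multivariate result.

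**The concern.** The change in a later-treated lesion from trial baseline to follow-up has two parts: what happened before its own course, and what happened after it. Only the second part bears on local response to that course. A lesion that grew under immune therapy and then shrank after radiation may be graded SD or PD. A lesion that shrank under immune therapy and did not change after radiation may be graded PR. A lesion absent at baseline has no denominator for a percentage change.

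At stake is the meaning of one covariate in the response models and nomogram, and of any table of local response by course. Section 13.3 does not say which irradiated lesion supplies the covariate when a patient has had several courses, so later lesions could enter it.

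**Working it through.** The plan states no figure that depends on this reference, so there is nothing to reproduce. The check applies the 11.2 cut-offs to the same lesion with two different references.

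**Inputs from the plan.** PR: diameter at most 0.7 times the reference. PD: at least 1.2 times the reference and at least 5 mm larger (11.2). irPD: SPD up by at least 25% from nadir (11.2).

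**Assumed input.** g, the fractional growth in diameter from trial baseline to the scan before the lesion's own course. The documents give no growth data, so a range is shown.

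**Formula.** Let B be the baseline diameter. Before the course the lesion measures B(1+g). After a shrinkage s it measures B(1+g)(1−s). PR against baseline requires (1+g)(1−s) ≤ 0.7, that is s ≥ 1 − 0.7/(1+g). PR against the pre-course scan requires s ≥ 0.30 for every g.

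| g | Shrinkage needed for local PR as written |
|---|---|
| −0.2 | 1 − 0.7/0.8 = 12.5% |
| −0.1 | 1 − 0.7/0.9 = 22.2% |
| 0 | 30% |
| 0.118 | 1 − 0.7/1.118 = 37.4% |
| 0.2 | 1 − 0.7/1.2 = 41.7% |
| 0.5 | 1 − 0.7/1.5 = 53.3% |
| 1.0 | 1 − 0.7/2.0 = 65.0% |

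The value 0.118 is anchored in the plan's own criteria. If baseline is the nadir and growth is uniform, a 25% rise in SPD is a rise in diameter of √1.25 − 1 = 11.8%.

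Larger g for one lesion is compatible with stable disease overall. Take two index lesions of 20 × 20 mm and 30 × 30 mm, so SPD = 400 + 900 = 1,300 mm². If the first grows to 30 × 30 and the second shrinks to 20 × 20, SPD is still 1,300 mm², yet the enlarging lesion has g = 0.5.

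**Illustrations (assumed diameters: baseline, before the course, after it).**
- 20, 30, 18 mm. As written: 18/20 = −10%, SD. Against the pre-course scan: 18/30 = −40%, PR.
- 20, 30, 30 mm. As written: +50% and +10 mm, PD. Against the pre-course scan: 0%, SD.
- 20, 40, 26 mm. As written: +30% and +6 mm, PD. Against the pre-course scan: −35%, PR. This is an extreme case.
- 40, 26, 26 mm. As written: −35%, PR. Against the pre-course scan: 0%, SD.

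**New lesions.** With no B, the percentage change is undefined. PR, SD and PD cannot be assigned; disappearance can still be judged.

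**Reach.** The irRC assessment in 11.2 covers non-irradiated lesions only, so local response does not enter ORR, and the sample size in 13.2 does not depend on it.

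**The case against.** The strongest reply is that little of this reaches a specified analysis. The synopsis lists the predictor analysis as exploratory. Section 13.1 frames the primary endpoint around the initial course, for whose lesion the baseline diameter is suitable. Responders get no further radiation until progression. Best overall response is recorded only until progression (11.2.1), so local response to the final course generally comes after the outcome being modelled. That leaves mainly patients in stable disease who are treated again before progression. If 13.3 were limited to the initial-course lesion, the models would be protected without touching 11.2. All of this stands and limits the weight of the point. It does not make the 11.2 rule correct for later lesions, and 13.3 contains no such limit.

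It can also be said that 11.2 does not spell out trial baseline. That is true, but no section offers a lesion-specific reference, and 11.1.1 and 11.1.2 point to the assessment before treatment.

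A reader might infer that all later-treated lesions are misgraded, or that local response to later courses is understated overall. The documents support neither. Both references agree when size did not change, and often give the same category when it did. The preference for an enlarging tumor is stated for mixed responses only. Prior shrinkage produces the opposite error, and without growth data the net direction cannot be determined.

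**Conclusion.** The point holds in limited form. As written, 11.2 can misgrade a lesion whose diameter changed between trial baseline and its own later course, and it cannot assign PR, SD or PD to a lesion new on study. For assumed growth of about 12% to 100%, the effective PR threshold is 37% to 65% shrinkage instead of 30%; for prior shrinkage it falls below 30%. This rests on reading baseline as the assessment before treatment, and on size changes that the documents do not quantify. The initial-course lesion is little affected.

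The consequence is confined to the predictor in 1.2 and 13.3, the nomogram, and descriptive reporting of later courses. It would be wrong to infer that the ORR, the two-stage decision or the sample size is compromised, or that new lesions have no usable criterion at all. The change is worth making because a stated rule gives wrong grades and is cheap to correct.

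**What to change.** In 11.2, take as reference for local PR the largest diameter on the last scan before the first fraction to that lesion, and state that this includes lesions first seen on study. For local PD, take the smallest diameter recorded from that scan onward, keeping the 20% and 5 mm conditions. This follows the smallest-measurement principle of 11.2.1 and 11.2.2. Using the pre-course diameter for PD as well would grade a lesion going from 40 to 20 and back to 40 mm as unchanged. CR stays as it is.

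In 13.3, define the local-response covariate as that of the initial-course lesion, in patients in whom that lesion is measurable and has been re-imaged.

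The cost is a sentence or two in each section. Later courses are already decided on follow-up imaging (5.3), and course dates and lesion location are already recorded (10.2, note 13), so no new procedure is needed. The downside is small: the covariate will be missing where the initial lesion is non-measurable (for example bone without a soft-tissue component, 11.1.2) or not re-imaged, and local responses to later courses will only be described.

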fractions or fewer is more immune-stimulatory, whereas a longer course of conventionally fractionated radiation is more immunosuppressive, through their differential effects on the up- and down-regulation of CD8 T-cells, Treg and MDSC cells, and expression of OX40, PD-L1, and MHC-1.²²⁻²⁴ Fractionated courses are also superior to a single fraction treatment in stimulating an abscopal effect.²² As such, for the purposes of this study, we will use a dose of 6-12Gy per fraction in 3 fractions (total dose 18-36 Gy) or 4-10 Gy per fraction in 5 fractions (total dose 20-50 Gy) to be completed over the course of 3-21 days. This variety of regimens offers a biologically effective dose (BED) range of 28-100 for early responding tissue (which correlates with tumor control) and 47-217 for late responding tissue (which correlates with side effects). This will give the treating physician a full range of options, such that an adequate dose can be given to the tumor while meeting all dose constraints of normal organs. The optimal hypofractionated radiation regimen is unknown, and there is some evidence that lower dose (and thus less ablative) regimens that would result in inferior local control may actually be more systemically immune-stimulating.²⁴ As such, regimens with a lower BED will be favored for this study, with the exception of situations in which improved local control to palliate symptoms is also a priority. Higher BED regimens may also be considered for larger size tumors and more rapidly growing tumors. This general preference for lower dose regimens will also have the favorable consequence of reducing the morbidity of therapy. Visceral metastases or metastases in organs involved in the immune system (e.g. liver) will be targeted preferentially over bone metastases due to the increased likelihood of an abscopal effect that has been previously reported for tumors in these sites.^{13-14, 25} If a bone metastasis requires treatment for palliative purposes we advise also treating a visceral metastasis concurrently. Brain metastases will be treated according to standard of care if they develop during the period of trial enrollment, but because there is little evidence to suggest that treating a brain metastasis can elicit an extracranial systemic response, we advise also treating a visceral metastasis concurrently to increase the likelihood of an abscopal effect.

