11.2.1. Best Overall Response

The best response recorded from the start of the treatment until disease progression/recurrence (taking as reference for progressive disease the smallest measurements recorded since the treatment started). The patient's best response assignment will depend on the achievement of both measurement and confirmation criteria.

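### Local progression of an irradiated lesion is measured from its baseline diameter, so regrowth after shrinkage can still be graded stable disease or partial response

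*Combined protocol and SAP*

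**What the plan says.** Section 11.2 grades irradiated lesions in a table of their own, introduced with the words "RECIST version 1.1 will be used to assess the local response of irradiated lesions only, taking as reference the baseline largest diameter". No row changes that reference:

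- PR is at least a 30% "decrease in the single largest diameter of the irradiated lesion".
- SD is "Neither sufficient decrease in diameter to qualify as PR nor sufficient increase in diameter to qualify as PD".
- PD is at least a 20% "increase in the single largest diameter of the irradiated lesion", together with an absolute increase of at least 5 mm. The row attaches the 5 mm to a sum, although section 11.1.2 makes one diameter the unit of measure.

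The plan's other progression rules use the smallest value. In the same section, irPD is at least a 25% "increase in tumor burden compared with nadir (at any single time point) in two consecutive observations at least 4 weeks apart". Section 11.2.1 defines best overall response "taking as reference for progressive disease the smallest measurements recorded since the treatment started", and section 11.2.2 gives the same reference for PFS in patients with CR or PR.

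Local response is assessed at baseline and follow-up (section 11.1.1). Sections 1.2 and 13.3 name it as a candidate predictor of response, and section 13.3 builds a nomogram from the multivariate model. Local control is not a listed endpoint.

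**The concern.** A baseline reference suits CR and PR, which describe shrinkage from the starting size. For PD it means that a lesion which has shrunk must first regrow to its starting size and then exceed it by 20% and 5 mm before progression is recorded. The more it shrank, the more regrowth goes unrecorded. Local PD is the only progression rule in the plan tied to baseline, and no reason is given.

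At stake are the local status recorded at follow-up scans, any descriptive account of local progression, and possibly one covariate in the response model. Section 11.2.3 plans a review of all responses at study completion, and that reviewer needs a single rule.

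**Working it through.** The plan gives no figure for this point, so there is none to reproduce. The check applies the table under both references.

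**Inputs from section 11.2.** PR at a decrease of 30% or more; PD at an increase of 20% or more and 5 mm or more; SD otherwise. Let B be the baseline diameter, N the smallest diameter (N ≤ B) and d the current diameter. Lesion sizes are illustrative assumptions. Where d meets both PR and PD, PD is taken to prevail.

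**Thresholds**

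- As written: PD when d ≥ max(1.2 × B, B + 5).
- From the smallest diameter: PD when d ≥ max(1.2 × N, N + 5).
- PR under either: d ≤ 0.7 × B.

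**Lesion with B = 50 mm, N = 20 mm**

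- PD as written: max(60, 55) = 60 mm, three times the smallest diameter.
- PD from smallest: max(24, 25) = 25 mm.
- PR limit: 0.7 × 50 = 35 mm.

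| d (mm) | From baseline | From smallest | As written | Smallest reference |
|---|---|---|---|---|
| 34 | −32% | +70%, +14 mm | PR | PD |
| 45 | −10% | +125%, +25 mm | SD | PD |
| 59 | +18% | +195%, +39 mm | SD | PD |

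**Other cases.** With B = 30 and N = 15 mm, PD starts at 36 mm as written and at 20 mm from the smallest diameter. A 50 mm lesion that disappears and recurs is PD only at 60 mm as written, against 5 mm.

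**Direction.** Since N ≤ B, 1.2 × N ≤ 1.2 × B and N + 5 ≤ B + 5, so the smallest-diameter threshold never exceeds the baseline threshold. A whole-millimeter grid (B from 10 to 100, N from 0 to B, d from N to 130; 496,041 combinations) agrees. No combination is PD as written and not PD from the smallest diameter. In 134,549 the written rule gives SD, and in 66,586 it gives PR, where the smallest-diameter rule gives PD. These are grid counts, not expected patient frequencies.

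**When PR and regrowth overlap.** This needs max(1.2 × N, N + 5) ≤ 0.7 × B. For B from 30 to 80 mm it is possible once the lesion has shrunk by about 42–47% or more; for B = 20 mm, by about 55%.

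**Delay, for illustration only.** Assume B = 50 mm and a volume doubling time of 60 to 180 days. Time from smallest size to PD = 3 × doubling time × log2(threshold / N).

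- N = 20 mm: 3 × 60 × log2(25/20) = 58 days, up to 174. As written: 3 × 60 × log2(60/20) = 285 days, up to 856.
- N = 35 mm: 3 × 60 × log2(42/35) = 47 days, up to 142. As written: 3 × 60 × log2(60/35) = 140 days, up to 420.

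**The case against.** **The smallest-value rule may already apply.** Sections 11.2.1 and 11.2.2 sit under 11.2, and 11.2.2 uses the labels CR and PR without the ir prefix. But both define patient-level outcomes. Patient-level progression follows irRC (section 3.3), and irradiated lesions are excluded from that assessment (sections 11.1.2 and 11.2). If these sections are nonetheless applied to irradiated lesions, they contradict the lead-in to the local table. Either way the text needs reconciling. What stands is that this looks more like loose drafting than a deliberate choice.

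**Little depends on local PD.** This stands. ORR and PFS rest on non-irradiated lesions under irRC, and section 5.3 ties further radiation to irRC categories.

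**The covariate may be unaffected.** This stands conditionally. If local response enters the model as best response, later regrowth does not change a PR or SD already reached. The plan does not say whether best or time-point response is meant.

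**Stronger readings that a reader might infer.** One is that the trial will report overstated local control; no such endpoint is planned. Another is that regrowth after shrinkage is the local failure the plan expects. Section 2.4 cites evidence that "lower dose (and thus less ablative) regimens that would result in inferior local control may actually be more systemically immune-stimulating", but it does not say how lesions fail. A lesion that only grows has its baseline as its smallest value, so both rules agree. A third is that many regrowths would never be graded PD. The documents hold no regrowth data, the fast-growth times above (140 and 285 days) are under a year, and section 10.2 continues imaging beyond 12 months before progression.

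**Conclusion.** The point holds as a defect in a stated definition. Followed as written, section 11.2 can grade clear regrowth of an irradiated lesion as SD or PR, and it can only under-call local progression. In the worked lesion the PD threshold is 60 mm instead of 25 mm.

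The effect is confined to time-point local status, descriptive reports of local progression and, unless it is coded as best response, the local-response covariate and the nomogram built from that model. The primary endpoint, PFS and the response-adapted radiation rule are untouched. The direction follows from the definitions alone. How many lesions would be misgraded cannot be computed, because the lesion sizes, depth of shrinkage and doubling times used here are assumptions.

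**What to change.** In section 11.2:

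- Keep the pre-radiation diameter as the reference for local CR and PR.
- Define local PD as *an increase of at least 20% and at least 5 mm over the smallest diameter of that lesion recorded since its radiation, counting the pre-radiation value if smallest*.
- Say that PD prevails when a lesion meets both PR and PD, as at 34 mm above.
- Replace *the sum* with *the diameter* in the PD row.
- Mark sections 11.2.1 and 11.2.2 as applying to the patient-level irRC assessment.

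In section 13.3, state whether the local-response covariate is best response or response at a named time point.

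The cost is a few sentences. The same scans and recorded millimeter values serve, so lesions already assessed can be re-graded. Reported local status may become slightly less favorable.
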